3.1.2.2. Adverse Events

AEs will be categorized according to MedDRA terms. AEs will be assessed from the time of informed consent signing through 1 month after study intervention administration.

AEs will be summarized by SOC and PT on a participant level.

The primary endpoints will be supported by summaries and listings of related AEs, severe AEs, and immediate AEs (within the first 30 minutes after administration).

AE reporting will be based on the specific reporting period. Standard algorithms for handling missing AE dates will be applied as described in the Pfizer Vaccine data standard rules as described in [Section 5.3](#).

3.1.2.3. Serious Adverse Events

SAEs will be categorized according to MedDRA terms. SAEs will be collected from the signing of the ICD through the end of the study (ie, 1 month after study intervention administration).

The safety endpoint “SAEs from administration through 1 month after administration” will be summarized by SOC and PT on the participant level.

3.2. Secondary Endpoint

3.2.1. Secondary Immunogenicity Endpoint

OPA GMT 1 month after study intervention administration

3.2.1.1. OPA Titers

OPA titers for [REDACTED] will be determined for all participants prior to study intervention administration at Visit 1 and at Visit 2 (approximately 1 month after Visit 1).

OPA titers above the LLOQ are considered accurate and their quantitated values will be reported. OPA titers below the corresponding LLOQ or denoted as BLQ will be set to $0.5 \times \text{LLOQ}$ for analysis. Missing assay results will not be imputed.

[REDACTED]

[REDACTED]

[REDACTED]

3.4. Baseline and Other Variables

Measurements or samples collected prior to the study intervention administration at Visit 1 are considered the baseline data for the assessments.

3.4.1. Demographics, Medical History, and Physical Examination

The demographic variables are age at the study intervention administration (in years), sex (male or female), BMI, race (Black/African American, American Indian, or Alaska Native, Asian, Native Hawaiian or other Pacific Islander, White), and ethnicity (Hispanic/Latino, non-Hispanic/non-Latino, not reported). In cases where more than 1 category is selected for race, the participant would be counted under the category “multiracial” for analysis.

Age at the time of administration of study intervention (in years) will be derived based on the participant's birthday. For example, if the administration day is 1 day before the participant's 19th birthday, the participant is considered to be 18 years old. For participants who were randomized but not administered a study intervention, the randomization date will be used in place of the date of administration for the age calculation. If the randomization date is also missing, then the informed consent date will be used for the age calculation.

Medical history will be categorized according to MedDRA.

3.4.2. Concomitant Vaccines and Concomitant Medications

The name and date of administration for all concomitant nonstudy vaccinations received and the concomitant medications used to treat SAEs from the time of signing of the informed consent through Visit 2 will be recorded on the CRF. Concomitant vaccines and concomitant medications will be coded using the WHO Drug Dictionary.

3.5. Safety Endpoints

AEs and SAEs are described above in the Primary Safety Endpoints section ([Section 3.1.2](#)).

4. ANALYSIS SETS (POPULATIONS FOR ANALYSIS)

Participant Analysis Set	Description
Enrolled	All participants who sign the ICD.
Randomized	All participants who are assigned a randomization number in the IRT system.
Evaluable immunogenicity	
Any participants who:
 
1. are eligible and randomized,2. receive the study intervention to which they are randomized,3. have at least 1 valid OPA titer or IgG concentration within 27 to 49 days, inclusive, after administration, and4. have no other major protocol deviations as determined by the clinician. 
The evaluable immunogenicity population will be the primary analysis population for OPA titer and IgG concentration

Participant Analysis Set	Description
	[REDACTED]
	[REDACTED]
Safety	All participants who receive the study intervention.

A major protocol deviation is a protocol deviation that, in the opinion of the sponsor's clinician, would materially affect assessment of immunogenicity, eg, participant receipt of a prohibited vaccine or medication that might affect immune response or a medication error with suspected decrease in potency of the vaccine. The sponsor's clinician will identify those participants with major protocol deviations before any unblinded analysis.

5. GENERAL METHODOLOGY AND CONVENTIONS

Methodology for summary and statistical analyses of the data collected in this study is described here.

In general, the study data will be summarized by study intervention group. CIs for all endpoints in the statistical analysis will be presented as 2-sided at the 95% level.

For all the OPA/IgG immunogenicity endpoints, the analysis will be primarily based on the evaluable immunogenicity population. [REDACTED]

Participants will be summarized according to the study intervention group to which they were randomized. Missing laboratory results will not be imputed.

The safety analyses are based on the safety population. Participants will be summarized according to the study interventions they received.

5.1. Hypotheses and Decision Rules

5.1.1. Estimands

The estimands corresponding to each primary, secondary, [REDACTED] objective are described in Table 2 in Section 2.2.

The estimands to evaluate the immunogenicity objectives are based on the evaluable immunogenicity population (Section 4). These estimands estimate the study intervention effect in the hypothetical setting where participants follow the study schedules and protocol requirements as directed.

Missing immunogenicity results will not be imputed.

5.1.2. Statistical Hypotheses

This is a Phase 1 study, and all the analyses are descriptive. No hypothesis tests are planned for this study.

5.2. General Methods

5.2.1. Analyses for Binary Endpoints

Descriptive statistics for categorical variables (eg, proportions) are the percentage (%), the numerator (n) and the denominator (N) used in the percentage calculation, and the 95% CIs where applicable.

The exact 95% CI for binary endpoints for each group will be computed using the F distribution (Clopper-Pearson method).¹

5.2.2. Analyses for Continuous Endpoints

Unless otherwise stated, descriptive statistics for continuous variables are n, mean, median, standard deviation, minimum, and maximum.

5.2.2.1. Geometric Means

For immunogenicity results of OPA titers and IgG concentrations, the GMs will be computed along with associated 95% CIs. The GM and the 95% CI will be calculated as the mean and the CI of the assay results on the natural logarithm scale and then exponentiating the results. Two-sided 95% CIs will be calculated based on the t distribution.

5.3. Methods to Manage Missing Data

A partial AE start date (missing day or missing both month and day) will be imputed by assigning the earliest possible start date using all available information, such as the stop date of the AE and the administration date(s) from the same participant, following the Pfizer standard of handling incomplete AE start dates. A complete missing start date for an AE is not allowed in the data collection.

The LLOQ for each assay will be provided by Vaccine Research and Development as part of the electronic data transfer or within the Clinical Testing Completion Memo prior to statistical analysis. Assay results above the LLOQ will be reported, and values below the LLOQ, denoted as BLQ, will be imputed as $0.5 \times \text{LLOQ}$ for analysis.

No additional imputation will be applied to other missing data.

6. ANALYSES AND SUMMARIES

6.1. Primary Endpoints

6.1.1. Local Reactions and Systemic Events

6.1.1.1. Main Analysis

- Estimands:
 - The percentage of participants reporting local reactions (redness, swelling, and pain at the injection site) within 7 days after administration ([Section 2.2](#)).
 - The percentage of participants reporting systemic events (fever, headache, fatigue, muscle pain, and joint pain) within 7 days after administration ([Section 2.2](#)).
- Analysis set: Safety population ([Section 4](#)).
- Analysis time point: Within 7 days after administration.
- Analysis methodology: For percentages of each group, the 2-sided Clopper-Pearson CIs will be calculated ([Section 5.2.1](#)).
- Reporting results: Count and percentage of participants with the indicated endpoint and the associated 2-sided 95% CI for each and any local reaction or systemic event after administration in each group will be provided by maximum severity across severity levels.

**Figures:**

Bar charts with the proportions of participants for each local reaction or systemic event on each day (Day 1 through Day 7) and any day (Day 1 through Day 7) will be plotted for each group, with different patterns displayed in the bar charts for different severity levels (each day) and different maximum severity levels (any day), respectively.

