8.3.1. Participant Electronic Diary

Participants will be asked to monitor and record local reactions and systemic events after vaccination (Day 1 through Day 7, where Day 1 is the day of study intervention administration) using an e-diary through an application installed on a provisioned device or on the participant's own personal device. This allows recording of these assessments only within a fixed time window, thus providing the accurate representation of the participant's experience. Data reported in the e-diary will be transferred electronically to the e-diary vendor, where they will be available for review by investigators, their appropriately qualified designees, and sponsor staff at all times via an internet-based portal. At intervals agreed to by the vendor and Pfizer, these data will be transferred electronically to Pfizer for analysis and reporting.

The daily e-diary data will not be captured in the CRF. However, if a participant is withdrawn because of prompted events reported in the e-diary, the event(s) should be recorded on the AE page of the CRF, regardless of whether the investigator considers the event(s) to be clinically significant.

The investigator or designee must obtain stop dates for any local reactions and specific systemic events that were ongoing on the last day that the e-diary was completed. The stop dates should be entered in the CRF.

Investigators (or an appropriately qualified designee) are required to review the e-diary data online at frequent intervals (daily is optimal) to evaluate participant compliance and reported events as part of the ongoing safety review.

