- Ask the participant to contact the site staff or investigator immediately if any significant illness or medical event (eg, emergency room visit or hospitalization) occurs.
- Provide the participant with the participant contact card containing the study and investigator information (see [Section 10.1.11](#)).
- Remind the participant to use appropriate contraceptives until 28 days after study intervention administration, if applicable.
- Schedule an appointment for the participant to return for the next study visit.
- Remind the participant to bring the e-diary to the next visit.
- The investigator or an authorized designee completes the CRF and the source documents and updates the study intervention accountability records.

PFIZER CONFIDENTIAL

- The investigator or appropriately qualified designee reviews the e-diary data online at frequent intervals (daily is optimal) for the 7 days (Day 1 is the day of study intervention administration) following administration to evaluate participant compliance and as part of the ongoing safety review.

8.10.2. Visit 2 – Follow-Up After Study Intervention Administration – 28 to 42 Days After Study Intervention Administration

- Ensure and document that the participant continues to be eligible for the study (see [Section 7](#) for participant discontinuation/withdrawal).
- Record nonstudy vaccinations, if applicable, as described in [Section 6.9](#).
- Discuss contraceptive use since Visit 1 (see [Section 10.4](#)), if applicable, and record any contraceptive use in the source documents.
- Review the participant's e-diary data. Collect stop dates of any e-diary events (local reactions or systemic events) ongoing on the last day that the e-diary was completed and record stop dates in the CRF.
- Collect the participant's e-diary or assist the participant in removing the study application from his or her own personal device.
- Determine if any AEs (including nonserious AEs and SAEs) have occurred since the previous visit, follow up on any previously reported events to determine the outcome (ie, record stop dates or confirm if they are still continuing), record such AEs as described in [Section 8.4](#), and record concomitant medications used to treat SAEs.

- [REDACTED]

- The investigator or an authorized designee completes the CRF and the source documents.

8.10.3. Unscheduled Visit for a Grade 3 Systemic Event or Suspected Grade 4 Reaction

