9.1.1. Estimands

The estimands corresponding to the primary and secondary objectives are described in the table in [Section 3](#). The estimands to evaluate the immunogenicity objectives will be based on the evaluable immunogenicity population (see Section 9.2 for definition). The estimands estimate the study intervention effect in the hypothetical setting where participants follow the study schedules and protocol requirements as directed. Missing serology results will not be imputed. Immunogenicity results that are below the LLOQ will be set to $0.5 \times \text{LLOQ}$ in the analysis.

In the primary safety objective evaluations, missing e-diary data will not be imputed. A partial AE start date (eg, missing day, missing both month and day) will be imputed by assigning the earliest possible start date using all available information (eg, stop date of AE, vaccination date from the same participant) following the Pfizer standards for handling incomplete AE start date. An AE with a completely missing start date is not allowed in the data collection. No other missing information will be imputed in the safety analysis..

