3.1.2.1. Local Reactions and Systemic Events

The local reactions, including redness, swelling, and pain at the injection site, and the systemic events, including fever, fatigue (tiredness), headache, muscle pain, and joint pain, are reported in the e-diary from Day 1 through Day 7 after administration, where Day 1 is the day of administration. The e-diary entries from the participant will be the primary data source for these events. However, any events related to administration that are considered local reactions or systemic events starting within 7 days after administration, that happen to be entered on the AE CRF, will be consolidated with e-diary data, and included in the reactogenicity summary. This section describes derivations with details for the assessment of the reactogenicity data: severity level, duration, and onset day.

Severity and Maximum Severity

The definitions for reactogenicity severity collected from the e-diary and from AEs are described in [Appendix 2](#).

For each local reaction or systemic event after administration, the maximum severity grade will be derived for the collection period (Day 1 through Day 7, where Day 1 is the day of administration) as follows:

maximum severity grade = highest grade (maximum severity) within 7 days after administration (Day 1 through Day 7) among severity grades reported for that local reaction or systemic event

Temperatures recorded in degrees Fahrenheit will be programmatically converted to degrees Celsius first for reporting. Fever will be grouped into ranges for the analysis according to Table 4. Maximum temperature range over the period from Day 1 through Day 7 will be mapped into the ranges described in Table 4 for summary of maximum temperature. For fever reported on the AE CRF within 7 days after administration, mild fever will be grouped in the $\geq 38.0^{\circ}\text{C}$ to 38.4°C range, moderate fever will be grouped in the $>38.4^{\circ}\text{C}$ to 38.9°C range, and severe fever will be grouped in the $>38.9^{\circ}\text{C}$ to 40.0°C range (unless specifically noted to be $>40.0^{\circ}\text{C}$ in an unplanned visit contact or noted on the AE CRF).

Table 4. Ranges for Fever

$\geq 38.0^{\circ}\text{C}$ to 38.4°C
$>38.4^{\circ}\text{C}$ to 38.9°C
$>38.9^{\circ}\text{C}$ to $40.0^{\circ}\text{C}^{\text{a}}$
$>40.0^{\circ}\text{C}^{\text{a}}$

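### Do the daily reactogenicity bar charts need a written rule for missed e-diary entries?

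*SAP*

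**What the plan says.** SAP section 6.1.1.1 sets the reactogenicity analysis on "Analysis set: Safety population", and SAP section 4 defines that set as "All participants who receive the study intervention". Having e-diary data is not a condition of membership. The estimand in SAP Table 2 is the percentage of participants given the intervention who report a reaction within 7 days.

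The Figures paragraph that follows calls for "Bar charts with the proportions of participants for each local reaction or systemic event on each day (Day 1 through Day 7", together with an any-day bar. SAP section 5.2.1 has percentages shown with "the numerator (n) and the denominator (N) used in the percentage calculation", but does not say who belongs in N when a day's entry is absent.

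On missing data, Protocol section 9.1.1 states: "In the primary safety objective evaluations, missing e-diary data will not be imputed". SAP section 5.3 adds no imputation beyond partial AE start dates and assay values below the quantitation limit.

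On data capture, Protocol section 8.3.1 says of the e-diary: "This allows recording of these assessments only within a fixed time window". At Visit 2 (Protocol section 8.10.2) sites obtain stop dates for events "ongoing on the last day that the e-diary was completed". SAP section 3.1.2.1 provides a second source: administration-related reactions starting within the 7 days "that happen to be entered on the AE CRF, will be consolidated with e-diary data, and included in the reactogenicity summary". SAP Appendix 2 adds unplanned assessments and takes the highest grade across sources.

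**The concern.** A rule against imputation fits two different programs. One keeps a participant with a missed day in N and adds nothing to the numerator, so the day is in effect shown as free of reaction. The other drops the participant from that day's N. Both comply with the text, and they give different bars.

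Missed days are foreseeable, because the entry window is fixed and the stop-date wording allows diaries to end on different days. If entries thin out during the week and N stays at all dosed, falling compliance can look like reactions resolving. If one group keeps its diary less well than another, it can look milder. These are primary safety endpoints, and Protocol section 9.5 says the data are meant to support a decision on further development.

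**Working it through.** **Inputs from the documents.** 45 participants per group (Protocol section 9.5; SAP Table 3); safety population; two-sided 95% Clopper-Pearson intervals (SAP section 5.2.1). The true reaction rate p and the number of missed entries k are not given. The values below are assumptions, with missingness independent of reaction.

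**The plan's own figure.** Protocol Table 5 uses 1 − (1 − p)^45. At p = 5% this gives 90.06%, which matches the stated 90.1%. The other four rows reproduce as well (59.71%, 74.61%, 84.07%, 93.82%). None of them depends on the denominator of a daily bar.

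**One daily bar on all dosed, with nothing recovered from other sources.** Expected height = p × (45 − k)/45. On participants with an entry that day, the expected height is p.

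| Assumed p | k = 2 | k = 5 | k = 9 |
|---|---|---|---|
| 60% | 57.3% | 53.3% | 48.0% |
| 30% | 28.7% | 26.7% | 24.0% |

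**Time course.** Take a flat true 30%, with 1, 2, 3, 5, 6, 8 and 9 entries missed on Days 1 to 7. The all-dosed bars read 29.3, 28.7, 28.0, 26.7, 26.0, 24.7 and 24.0%. The decline comes entirely from the chosen schedule of missed entries.

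**Two groups.** Both have a true rate of 60%, with 5% and 15% of entries missed: 0.60 × 0.95 = 57.0% and 0.60 × 0.85 = 51.0%.

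**Any-day table, which carries the primary estimand.**
- If m participants have no diary and a fraction c of their reactions reaches the AE CRF, the shortfall is p × m × (1 − c)/45. With p = 60% and c = 0, this is 2.7 points for m = 2 and 6.7 for m = 5. With c = 1 it is zero.
- If each day is missed independently with probability q, a reaction lasting d days is lost with probability q^d, so the shortfall is p × q^d. With p = 60% and q = 10%, this is 6.0 points for d = 1, 0.6 for d = 2 and 0.06 for d = 3.

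**Scale.** The 95% interval for 27/45 (60.0%) is 44.3% to 74.3%, which is 30.0 points wide.

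**Would changing the daily denominator help?** Suppose daily bars used participants with an entry while the any-day bar stayed on all dosed. Let 24 people react on a day with 40 entries, and nobody else react that week. The daily bar is 24/40 = 60.0% and the any-day bar is 24/45 = 53.3%. A single day would then exceed the whole week in the same chart.

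**The case for a change.** The case for amending the SAP is a fair one. The gap is real in the readable text, two programmers could produce different bars, and the remedy is a few sentences with no new data. The all-dosed error has one direction, and a confidence interval does not reveal a systematic shift. An N of 45 under every bar also hides how many participants supplied data that day. If each entry were missed independently at an assumed 2%, 5% or 10%, the expected number missing at least one of seven days would be 45 × (1 − (1 − q)^7) = 5.9, 13.6 or 23.5 per group.

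Much of this stands: a count of entries per day would be useful beside the figure. Four things limit it.

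- For the any-day table the documents already answer the question. The estimand counts people dosed and asks what percentage report a reaction, so someone who reports nothing is in N and not in n.
- SAP section 3.1.2.1 announces derivations for severity, duration and onset day, but only severity can be read before the blacked-out text. A day-level rule could sit there, and redacted text cannot be counted as absent.
- Missed entries may be few or partly recovered. Sites review the diary online, ideally daily; Protocol section 4.1 has Visit 2 follow up the e-diary as needed; and AE-CRF and unplanned records are merged in.
- The obvious amendment has costs. As shown above, with-entry daily bars beside an all-dosed any-day bar can contradict each other. Moving AE-CRF-only reactions to a footnote would conflict with the SAP's instruction to include them in the reactogenicity summary.

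**Conclusion.** No change to the plan is needed. The SAP fixes the population for the primary percentages, and the open point is the N under a daily bar in a descriptive figure. With no hypothesis test (Protocol section 9.1; SAP section 5.1.2), any effect is on how the bars are read. At 2 of 45 entries missed and a true rate of 60%, a daily bar shifts by 2.7 points. It shifts by 6.7 points at 5 missed and 12.0 at 9 missed (60.0 − 48.0). Those figures rest on assumed rates, missingness unrelated to reaction and no recovery from other sources, so the actual effect is unknown and is small if compliance is good. The analysts can settle it in the figure shell by using one basis for the daily and any-day bars, keeping AE-CRF reactions in, and showing how many participants had an entry each day. The conclusion would be weaker if many entries were missed, or if missed entries differed clearly between groups. The online compliance review would bring either to light.
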